Examine moderators. For the direct effects of condition (UC, MRT) on study outcomes (overall risk for recidivism; and substance use, mental health, housing, and employment status), we will test three moderators of these effects: (a) incarcerated or not in the past 12 months; (b) number of months since the most recent criminal justice event (i.e., charged or released from incarceration); (c) an index of extent of criminal history (i.e., a z-scored composite of number of charges, number of times incarcerated, and total number of months incarcerated in lifetime). The continuous moderators (number of months since the most recent criminal justice event, and index of criminal history) will be zero-centered. The main effects of these moderator variables and the interaction terms between condition (UC, MRT) and each moderator will be entered into the same regression models described above. If any interaction terms are significant, conditional moderators will be evaluated to assess the direction and magnitude of effects within subgroups (e.g., re-entry subgroup).

Examine mechanisms (i.e., reasons MRT is effective). MH RRTP completion (yes/no) and SUD/mental health continuing care utilization (outpatient attendance [yes/no] and amount; mutual-help group attendance [yes/no], number of meetings) will be examined as mediators between condition and risk for recidivism, and between condition and the health-related outcomes at the 6- and 12-month follow-ups. We will conduct regression models that correspond to a hypothesized causal sequence among (1) MRT, (2) one of our hypothesized mediators, and (3) better outcomes. In each model, we will control for relevant covariates (e.g., baseline values for sociodemographics and the dependent variable). In the first regression, a dummy variable representing the MRT intervention will be the independent variable and the dependent variable will be the outcome (e.g., PICTS GCT scores). In the second regression, MRT will be the independent variable and the dependent variable will be the potential mediator. In the third regression, the potential mediator will be the independent variable and the dependent variable will be the outcome. If the coefficient for MRT or a potential mediator is significant in all of these cases, we will proceed. In the final regression, the MRT dummy variable will be entered simultaneously with the potential mediator as predictors of the outcome. If the coefficient for the potential mediator is significant and the coefficient for the MRT dummy variable on the outcome is reduced, we will conclude that mediation is supported and will evaluate whether the indirect effect is significant. To account for variability in intensity of continuing care services, we will test for significant interactions on outcomes between our measures of continuing care and a variable for site.

We will also determine if any significant, direct effects of MRT on (a) overall risk for recidivism, and (b) the health-related outcomes, are mediated by specific mechanisms of MRT (i.e., improvements in interpersonal functioning and reductions in affiliations with antisocial and substance abusing peers). We will conduct GLMM regression models that correspond to a hypothesized causal sequence among (1) MRT (vs. UC), (2) the potential mechanisms, and (3) one of the outcomes, and control for covariates. Finally, we will conduct regression analyses

(controlling for relevant covariates) to examine associations of MRT dose (number of group sessions attended; number of steps completed) with patient outcomes at the follow-ups. Based on prior work and the recommendations of VJP Specialists who have previously conducted MRT groups with Veterans, we will explore whether completion of 12 sessions is as effective as a full dose (24 sessions).

Adjust for contamination and missing data. To address the possibility of contamination, if we learn that MRT-related information was shared with UC participants, the records of those UC participants will be flagged, and contamination-adjusted intention-to-treat analyses will be calculated (i.e., the effect of treatment assignment on outcomes is adjusted by the percentage of participants assigned to the UC condition who may have received the treatment). To minimize missing data, we will train research assistants on the importance of completing each item while respecting the rights of patients to refuse answers. Based on our prior studies, we expect to achieve less than 5% missing data on each variable at each assessment, over and above any attrition. We will obtain as high a follow-up rate as possible at each assessment. In contrast to MH RRTP completion and SUD/mental health continuing care utilization, which will be collected primarily via VA administrative data at the 6- and 12-month follow-ups, data on recidivism risk and health-related outcomes at the follow-ups will be collected via patient reports, and will therefore have more missing data due to expected attrition at those time points. GLMM's strengths are the ability to use all available data, including data on respondents who may not have provided data at each assessment. All patients who enter the study will be included in GLMM analyses. However, we will also conduct analyses that include only patients who attended at least the first MRT session. We will use a model-based multiple imputation procedure and will impute missing values using least-squares regression imputation. We will select a set of measures that are associated with the variable at issue and use it in a series of iterated least-squares regression models to generate a predicted value for the variable being imputed, and then substitute the missing value with the predicted value.

**Aim 2: Analytic plan.** De-identified audio-files of the staff and patient interviews will be transcribed. The transcription will be performed by a professional medical transcription agency specifically chosen for this study. Drs. [name] and [name] will review the transcripts of these interviews, and take detailed notes using the structure of the RE-AIM Planning Tool. With feedback from project team members, we will create tables to summarize and categorize the barriers/facilitators of MRT implementation at the system, provider, and patient levels, and include potential solutions and potential-to-leverage columns that contain evidence-based implementation tools to be considered for more widespread usage of MRT. These analyses will reduce and display the data. In conjunction with the tables, we will identify a small set of themes within each domain of the RE-AIM framework that signify triangulated findings (e.g., factors that would facilitate and maintain a program's use of MRT in a way that fits within the clinical and administrative infrastructure of the facility). The purpose will be to capture in-depth information on patient, provider, and contextual factors that will facilitate or hinder the successful implementation of MRT. Such factors will be used to inform post-hoc interpretation of project findings and guide development of action plans to be tested in subsequent implementation projects. If Aim 1 hypotheses are not supported, we will use this analytic approach to identify barriers associated with delivery of MRT during the RCT, and what modifications to MRT could

be made to maximize effectiveness. Such information will be shared with our operational partners to guide their future efforts to reduce recidivism risk among JIVs.

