Health-related functioning. We will use the ASI to assess substance use, and mental health, housing, and employment status at baseline. In addition to items on housing, the ASI assesses functioning in several problems areas, e.g., alcohol use, drug use, psychiatric, and employment. In each domain, items measure the number, extent, and duration of problems (lifetime and past 30 days). Composite scores are produced from sets of items that are standardized and summed (range from 0 to 1; higher scores indicate poorer outcomes), which provide internally-consistent indices of patient status in the relevant domains in the past 30 days. Prior work supports the validity of self-reports on these areas. To further assess substance use, the Time-Line Follow Back (TLFB) will be administered. The TLFB is a retrospective, calendar-based measure of substance use, which has been validated for administration in-person or via phone and will provide information on quantity and frequency of substance use in the 6 months prior to the baseline assessment (i.e., percent days of use; percent days abstinent; most consecutive days using; most consecutive days abstinent). To further assess psychiatric status, the PHQ-9 will be administered to assess symptoms of major depression, and the PTSD Checklist (DSM-V version) will be used to assess symptoms of PTSD. VA records will be used to gather SUD and mental health diagnoses on patients at the time of admission to the MH RRTP, per ICD-9 codes linked to the appropriate bedsection code in the inpatient files.

SUD/mental health treatment and mutual-help history. We will use the ASI to assess participants' treatment history (i.e., any care [yes/no]; number of visits over the lifetime and past 12 months) for SUD (outpatient, residential, pharmacotherapy) and mental health (outpatient, inpatient, residential). Information on VA health services utilization in the past 12 months will be collected via patient records for these domains of care. Data on non-VA health care utilization will be collected to help determine whether the two condition arms are balanced and ensure that any changes in utilization of VA services are not due to changes in non-VA care. To measure attendance (yes/no; number of meetings) and involvement in mutual-help groups (lifetime, past 12 months) we will use items from the Alcoholics Anonymous Inventory.

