MH RRTP completion and SUD/mental health continuing care utilization. MH RRTP completion will be determined from VA administrative databases. Data on SUD/mental health continuing care utilization since the prior assessment will be obtained from (a) VA administrative databases, for VA care; (b) an interview on non-VA health care utilization, for non-VA care; and (c) the Alcoholics Anonymous Inventory for mutual-help group attendance. From these data sources, we will calculate whether SUD/mental health care was received (yes/no) and the amount of care received (number of outpatient visits; number of mutual-help group meetings). To be comprehensive, we will also assess whether SUD or mental health inpatient/residential care occurred since the prior assessment (i.e., any care [yes/no], number of bed days of care).

MRT mechanisms. We will re-administer the measures used at baseline to assess interpersonal functioning and affiliations with antisocial and substance abusing peers.

Measuring utilization of VA health care services. We will collect data on patients' use of VA health care (SUD; mental health) to test our hypothesis (i.e., effects of MRT will be mediated in part by service utilization). National data extracts from the Patient Treatment Files (PTF) and National Patient Care Databases (NPCD) will be used to determine utilization of VA residential (MH RRTP) and outpatient care. Corresponding information on utilization of VA-paid care at non-VA facilities is available in the national Fee Basis files and will be searched for all study participants. These datasets are maintained at VA's Corporate Data Warehouse and available, in SAS format by fiscal year, through

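### The mediator-to-outcome regressions are not committed to adjusting for the baseline level of the mediator, although it is collected for most mediators

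*Combined protocol and SAP*

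**What the plan says.** Under the mechanisms heading of section 5.6, MH RRTP completion, outpatient continuing care and mutual-help attendance are tested as mediators through four regressions. On covariates the plan says that each model will "control for relevant covariates (e.g., baseline values for sociodemographics and the dependent variable". The list is given as examples.

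The first regression takes the outcome on MRT. In the second, "MRT will be the independent variable and the dependent variable will be the potential mediator". For the third: "In the third regression, the potential mediator will be the independent variable and the dependent variable will be the outcome". In the final one, "the MRT dummy variable will be entered simultaneously with the potential mediator as predictors of the outcome". Mediation is declared supported on this condition: "If the coefficient for the potential mediator is significant and the coefficient for the MRT dummy variable on the outcome is reduced". The significance of the indirect effect is evaluated after that conclusion.

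A separate paragraph covers the MRT mechanisms, namely interpersonal functioning and affiliation with antisocial or substance-using peers. It gives no covariate list beyond saying that covariates will be controlled. It words the mediators as improvements and reductions, without saying whether level or change enters the model.

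Section 5.5 collects the baseline counterparts. On service use: "Information on VA health services utilization in the past 12 months will be collected via patient records". On the mechanisms: "We will re-administer the measures used at baseline to assess interpersonal functioning and affiliations with antisocial and substance abusing peers".

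**The concern.** Randomisation makes the arms comparable. It does not make patients with high and low mediator values comparable. A Veteran who attended a lot of outpatient care or many mutual-help meetings before admission is likely to do so afterwards, and may do better for reasons unrelated to that attendance. If the prior level is left out of the regression of outcome on mediator, the mediator coefficient partly measures who the patient already was.

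The conditional rule under baseline equivalence in section 5.6 does not close this gap. It brings in prior treatment use and mutual-help participation only if the arms differ on them. A perfectly balanced trial would leave them out, and the mediator-outcome path would still be confounded.

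At stake is hypothesis 1c and the secondary account of how MRT works. An effective treatment could be credited to the wrong pathway, and implementation advice would then be built on that pathway.

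**Working it through.** **1. What the baseline dependent variable means in each regression**

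| Regression | Dependent variable | Predictor of interest | Baseline covered by the named examples |
|---|---|---|---|
| First | Outcome | MRT | Outcome |
| Second | Mediator | MRT | Mediator, where one exists |
| Third | Outcome | Mediator | Outcome only |
| Final | Outcome | MRT and mediator | Outcome only |

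The gap is in the third and final rows.

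**2. What is collected at baseline (section 5.5)**

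- Outpatient care: ASI treatment history (lifetime and past 12 months), VA records for the past 12 months, and non-VA use.
- Mutual help: attendance and involvement, lifetime and past 12 months.
- Interpersonal functioning and peer affiliations: measured at baseline and repeated at follow-up.
- MH RRTP completion: an event of the index stay, so it has no baseline level. The nearest proxy is prior residential treatment on the ASI.

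**3. Size of the spurious coefficient**

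The plan gives no figure for the mediation analysis, so there is none to reproduce. From the power section: 292 analysed (365 × 0.80) and two-sided alpha .05. Everything else is assumed. With M0, Y0 the baseline and M1, Y1 the follow-up mediator and outcome, each with SD 1 within arm:

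- M1 = .6·M0 + a·MRT + error
- Y1 = .5·Y0 + .15·M0 + 0·M1 + c·MRT + error
- corr(M0, Y0) = .3

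The true mediator effect is zero. In the final regression without M0, the mediator coefficient is .15 × cov(M0, M1 | Y0) / var(M1 | Y0):

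- covariance: .6 × (1 − .3²) = .546
- variance: 1 − (.6 × .3)² = .9676
- coefficient: .15 × .546 / .9676 = .085

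For the standard error, the explained variance of Y1 is .25 + .0225 + 2 × .5 × .15 × .3 = .3175, leaving .6825. The omitted part of M0 adds .0225 × (.91 − .546²/.9676) = .0135, giving .696. SE = √(.696 / (292 × .9676)) = .050, so z is about 1.7. The coefficient is then significant in about 40% of trials by normal approximation, and about 38% by simulation. With M0 in the model the coefficient is 0 and the rate about 5%.

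**4. The full four-step rule**

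The plan also requires MRT to be significant for the outcome and for the mediator, and the MRT coefficient to shrink. Treating the steps as roughly independent:

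- MRT on outcome, c = 0.4: SE = √((.6825 + .0225 × .91) × 4/292) = .098, z = 4.08, power .98.
- MRT on mediator, a = 0.3: SE = √(.64 × 4/292) = .094, z = 3.2, power .89. For a = 0.5, power is close to 1.

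| MRT effects | Approximation | Simulated |
|---|---|---|
| Both, a = 0.3 to 0.5 | .98 × .89 × .38 = 33% to .98 × .38 = 37% | about 34% to 37% |
| Neither | .05 × .05 × .38 = 0.1% | 0.1% |
| Outcome only | .98 × .05 × .38 / 2 = 0.9% | 0.9% |
| Mediator only, a = 0.3 | .05 × .89 × .38 / 2 = 0.8% | 0.7% |
| Both, baseline mediator added | .98 × .89 × .05 / 2 = 2.2% to .98 × .05 / 2 = 2.5% | about 2% |

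The division by 2 applies where a chance result must fall in the direction that shrinks the MRT coefficient. Repeat simulations of the first row ran from 33% to 39%. With a = 0.5, a path of .10 instead of .15 gives 19%, and .20 gives 62%. Also requiring a Sobel test of the indirect effect lowers the a = 0.3 result to 17%.

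**5. A less favourable model**

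The fix works completely in steps 3 and 4 only because an error-free baseline mediator is the sole confounder. A second simulation used a stable trait measured with error (trait-outcome loading 0.2 to 0.6, mediator stability 0.5 to 0.7, same MRT effects). False support was 31% to 99% with the named covariates and 12% to 70% after adding the baseline mediator. The spurious coefficient shrank by roughly 28% to 41%. When MRT did not move the mediator, the named-covariate sequence passed in 1% to 3% of trials.

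**The case against.** The strongest reply is that the covariate list is open. Sociodemographics and the baseline dependent variable are examples, so an analyst could add the baseline mediator and remain within the plan. That stands as to wording: the covariate is unspecified, not excluded. But an open list leaves the choice until the data are in hand, on a path where the choice can decide the result.

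Two further points stand in full. The second regression already covers the baseline mediator, because there the mediator is the dependent variable. And the examples belong to the service-use models. A reader might infer that the mechanism models also adjust for demographics and baseline outcome while omitting the baseline mediator, but the text gives those models no list at all. Their mediators are worded as change and the measures are repeated, so the baseline may enter through a change score.

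A reader might also take the 38% rejection rate of the mediator coefficient as the plan's false-mediation rate, or think that any arm difference in the mediator is enough. The documents do not support either. The sequence also requires a significant MRT effect on the outcome and on the mediator, and without both it almost never passes.

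Finally, all the inputs other than sample size and alpha are assumed, and they treat the mediators as continuous, whereas several are yes/no or counts. That limits the figures to illustration.

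**Conclusion.** The point holds in a limited form. The plan does not commit the third and final service-use regressions to the baseline mediator, and it leaves both covariates and mediator form unstated for the mechanism models. The consequence is misattribution of the pathway when MRT changes both mediator and outcome, which is the situation hypothesised. The illustrated size is about 34% to 37% false support against about 2% with the covariate added. This rests on the assumed stability of .6, path of .15 and MRT effects, with a true mediator effect of zero.

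It would go too far to infer that a stable trait alone can produce a mediation finding, or that adding the covariate cures the problem. The first fails on the plan's own sequence, the second when the baseline measure captures the trait with error. This affects secondary hypothesis 1c and the mechanism analyses. The comparisons for 1a and 1b do not depend on it.

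**What to change.** In the mechanisms part of section 5.6:

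- Third and final regressions: name the baseline measure that matches the mediator, alongside the baseline outcome. This is prior-12-month VA and non-VA SUD/mental health care for continuing care, and prior-12-month mutual-help attendance for mutual help.
- MH RRTP completion: use prior residential treatment history from the baseline ASI, described as a proxy.
- Mechanism GLMMs: include the baseline interpersonal-functioning or peer-affiliation score together with the baseline outcome, and state whether the mediator enters as level or as change.
- State that this reduces but does not remove mediator-outcome confounding. A sensitivity analysis for unmeasured confounding would complement it.

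The second regression needs no change where a baseline level exists. The cost is a few lines of text and one already-collected covariate per model, with no new data collection and no change to sample size.

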### 3.0 Objectives

Using the new Veteran-specific manual, the overarching objective of the current proposal is to implement and evaluate Moral Reconciliation Therapy (MRT) as an intervention to reduce risk for criminal recidivism and improve health-related outcomes among justice-involved Veterans (JIVs) in VA Mental Health Residential Rehabilitation Treatment Programs (MH RRTPs). Using an effectiveness Hybrid Type 1 design, which incorporates both an RCT and a formative evaluation to facilitate future implementation, we will address two specific aims in this proposal:

**Aim 1:** At three VA facilities (Palo Alto, Little Rock, and Bedford), randomize to MRT or usual care a total of 365 Veterans who (a) are being admitted to an MH RRTP in VA, and (b) had been arrested and charged and/or released from incarceration in the past 5 years. We hypothesize that, during the 12-month study period, those who receive MRT, relative to those who receive usual care, will:

**(1a)** have a lower overall risk for criminal recidivism, operationalized via total scores on the General Criminal Thinking (GCT) index of the Psychological Inventory of Criminal Thinking Scale (PICTS),

**(1b)** have better health-related outcomes (substance use, mental health, housing, and employment), and.

**(1c)** the effects of MRT on reduced risk for recidivism and better health-related outcomes will be mediated in part by greater likelihood of completing the MH RRTP and utilizing substance use disorder and mental health continuing care services.

**Aim 2:** Use the RE-AIM (Reach, Effectiveness, Adoption, Implementation, Maintenance) framework to conduct a formative evaluation of MRT (i.e., qualitative interviews with providers and patients). Such information will provide guidance to our operational partners in terms of broader adoption of MRT in VA, particularly with regard to identifying:

**(2a)** barriers and facilitators to implementing MRT in MH RRTPs across VA.

**(2b)** whether and/or how to adapt MRT for diverse subpopulations of Veterans (e.g., OEF/OIF Veterans; women; racial/ethnic minorities; those with PTSD).

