## 5.6 Data Analysis

**Sampling plan: Power analysis.** To ensure sufficient variability in our outcomes, and in turn increase the power to test study hypotheses, we focused our Specific Aims on overall risk for recidivism (i.e., PICTS GCT total scores) and functioning on health-related risk factors, rather than recidivism per se (e.g., rearrest), as the latter may have a low base rate within the 12-month study period. Based on meta-analyses and studies of MRT mechanisms, we expect a medium effect size (Cohen's  $f^2=.15$ ) in multiple regression models testing condition (UC vs. MRT) as a predictor of recidivism risk and the health-related outcomes. However, given the planned moderation analyses, we calculated the power to detect small effect sizes (i.e.,  $f^2=.02$ ). To account for having patients at three sites, power analyses using G\*Power were based on having six cells (two conditions per site). A sample size of 292 (146 in each condition) will provide 80% power to detect a small effect size at an alpha of .05 (two-tailed test). To account for the moderators, we calculated the available power and effect size that could be detected in a regression model, given (a) our projected sample size, and (b) the addition of six more predictors in the model (i.e., the three moderator variables listed above and three interaction terms between these moderators and the variable of condition). Based on an N of 292 and alpha of .05, we would have 80% power to detect an  $f^2$  of .07, a small-to-

medium size effect. We are predicting 20% attrition at the follow-ups. This was the rate of attrition in prior longitudinal studies of project team members of Veteran treatment samples with high rates of criminal histories. Thus, we will recruit a total of 365 patients (183 in each condition, with rounding). If attrition reaches 30%, we will still have 80% power to detect an  $f^2$  of .08.

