Examine baseline equivalence. We will use independent group t-tests and chi-square tests for continuous and categorical variables, respectively, to determine whether patients assigned to the UC and MRT conditions are comparable at baseline on (a) age, race/ethnicity, marital status, education, and income; (b) PICTS GCT scores; (b) substance use, mental health, housing, and employment status; (c) SUD/mental health treatment utilization and mutual-help group participation; and (d) percent incarcerated in the past 5 years, number of months since the most recent criminal justice event (i.e., charged or released from incarceration), and extent of criminal history (i.e., scores on a composite of number of charges, number of times incarcerated, and total number of months incarcerated). We do not anticipate baseline differences; however, if they are detected, the variables on which groups differ will be controlled in the regression analyses.

Compare the UC and MRT conditions on study outcomes. We will use GLMM regressions to compare the UC and MRT conditions on overall risk for recidivism (PICTS GCT scores); and substance use (ASI alcohol and drug composites; TLFB scores), mental health (ASI psychiatric composite; PHQ-9 and PCL-5 scores), housing (ASI–number of months in a stable residence), and employment status (ASI employment composite) over the study period. GLMM models permit modeling of repeated-measures data; do not require that all participants be measured at all time points to be included in analyses; and apply to continuous, dichotomous (e.g., MH RRTP completion), and Poisson-distributed outcomes (e.g., number of SUD/mental health outpatient visits).

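### Hypothesis 1c is tested on about 90 mediation chains with no lead chain and no error control, and mediation is declared before the indirect effect is tested

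*Combined protocol and SAP*

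**What the plan says.** Section 3.0 lists 1c among the three Aim 1 hypotheses. For recidivism risk and the health measures alike, it holds that what MRT achieves "will be mediated in part by greater likelihood of completing the MH RRTP and utilizing substance use disorder and mental health continuing care services". The Abstract and the Aim 1 analytic plan in section 5.6 repeat it. None of the three places calls it exploratory, although section 5.6 does use the language of exploration for the dose question.

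The mechanisms paragraph of section 5.6 gives the test.

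- The mediators are programme completion and continuing care. Outpatient care and mutual-help groups are each taken in two codings, as any attendance and as an amount.
- They are examined for recidivism risk and "between condition and the health-related outcomes at the 6- and 12-month follow-ups".
- Each causal sequence contains "2) one of our hypothesized mediators", so the mediators are taken singly.
- Three regressions must each be significant: MRT on outcome, MRT on mediator, and mediator on outcome.
- In a fourth regression with both predictors, the mediator must again be significant. If it is, and "the coefficient for the MRT dummy variable on the outcome is reduced, we will conclude that mediation is supported". The same sentence then adds that the significance of the indirect effect will be evaluated.

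Section 5.5 re-measures the utilization mediators for each interval: "Data on SUD/mental health continuing care utilization since the prior assessment will be obtained from" three sources, namely VA databases, an interview and a mutual-help inventory.

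**The concern.** Every chain can end in a stated verdict that mediation is supported, and the plan does not say which chain, or how many, decide 1c. Some chain may pass by chance and be reported as support for a formal hypothesis. The indirect effect is the quantity that mediation is about, yet its test follows the verdict, so as written it does not gate the claim.

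The trial is a Hybrid Type 1 study meant to guide adoption in VA. If it reported that MRT works through programme completion or continuing care when MRT changes neither, implementers would put their effort in the wrong place.

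**Working it through.** **The plan's own figures.** The plan states no error rate for the mediation tests, so there is none to reproduce. The sample-size paragraph gives 292 evaluable patients (146 per arm) for "80% power to detect a small effect size at an alpha of .05 (two-tailed test"), inflated for 20% attrition: 292 / (1 − 0.20) = 365, which reproduces. Here 292 is used only as the number analysed. Whether it delivers 80% power is a separate question.

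**Step 1: count the chains.**

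| Element | Source | Count |
|---|---|---|
| Mediators: completion; outpatient care yes/no; outpatient amount; mutual-help yes/no; number of meetings | 5.6, mechanisms | 5 |
| Outcomes: "overall risk for recidivism (PICTS GCT scores"), ASI alcohol, ASI drug, TLFB, ASI psychiatric, PHQ-9, PCL-5, housing, employment | 5.6, comparison of conditions | 9 (12 if the four TLFB scores in 5.5 are separate) |
| Visits: 6 and 12 months | 5.6, mechanisms | 2 (1 if both share one model) |

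5 × 9 × 2 = 90; 5 × 9 × 1 = 45; 5 × 12 × 2 = 120. The interpersonal and peer mechanisms in the next paragraph of section 5.6 are not counted.

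**Step 2: closed-form orientation.** Assume MRT affects nothing, all tests are independent, and the mediator-outcome steps and the reduced-coefficient condition are ignored. The chance of at least one false MRT-to-mediator result together with at least one false MRT-to-outcome result is:

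- 18 outcome tests: (1 − .95^5) × (1 − .95^18) = .226 × .603 = 13.6%
- 24 outcome tests: .226 × (1 − .95^24) = 16.0%
- 9 outcome tests (visits pooled): .226 × (1 − .95^9) = 8.4%

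The tests are in fact correlated and the omitted steps block some claims, so the full rule has to be simulated.

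**Step 3: simulate the full rule.** Assumptions, none of them given in the documents except N and f²: N = 292, 1:1; every regression tested at two-sided .05 (the plan states .05 only for sample size); continuous mediators; effect on outcomes d about 0.28 (2 × √.02 = 0.283). In the runs with a stated r, correlations are .5 among mediators and among outcomes, and r is the absolute mediator-outcome correlation. Other runs used different correlation structures. All four steps and the reduced-coefficient condition are applied.

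*MRT improves outcomes but changes no mediator; chance that at least one chain is declared:*

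- 90 chains, r = .25: 13.0–14.3% in separate runs
- r = .10, .15, .35: 10.2%, 13.4%, 13.6%
- Effect on PICTS GCT only: 16.6–17.6%
- Mediator correlation .7: 10.0–12.3%
- The two codings of the same care correlated .85: 11.2%
- One visit (45 chains): 8.8–9.9%

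With a significant Sobel indirect effect also required, r = .25 gives 9.6–11.1%, codings correlated .85 give 7.8%, one visit gives 6.8%, and r = .15 gives 5.1%. At r = .10 it falls to 2.8%.

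*MRT affects nothing:* 0.6–1.3% for r of 0 to .05, 4.5–6.7% at .15, and about 8–12% for .20 to .35.

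*Finer splitting* (nine mediators, an assumption) gives 22–26% when outcomes improve and 16–19% when MRT affects nothing.

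**Step 4: what naming chains in advance does.** Under the plan's own four-step rule, with MRT improving outcomes but no mediator, one pre-named chain gives about 2% (range 1–2.6%). Two named chains without adjustment give about 3.5–4.7%. If instead two indirect effects are tested by joint significance of the two paths, with no total-effect step, the rate is 9.3% unadjusted and 4.9% with Holm.

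**The case against.** The strongest reply is that the causal-steps rule is already restrictive. A chain goes forward only if MRT has a significant total effect on that outcome, and the other steps must also pass. If MRT affects nothing and mediators are weakly related to outcomes, the false-claim rate is below 5%. This is right, and it is why the size must be a range. It helps less in the situation the plan expects, where MRT improves outcomes. A real total effect then opens the first step, and a moderate mediator-outcome correlation opens the third. Only the repeated MRT-to-mediator tests remain as protection.

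The second reply is that the plan does test the indirect effect. That is so, and a reader should not infer that the test is missing. The defect is its order: the conclusion comes first. Making the test a condition lowers the rate to about 5–12% for r of .15 or more.

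The third reply is that 90 overstates the effective number. The yes/no and amount codings overlap heavily, and the repeated-measures models elsewhere in section 5.6 could be read as pooling the visits. Both points lower the rate, to about 9–11%, without removing the problem.

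Two stronger readings are tempting. One is that a false mediation claim is three times likelier than 5%. That is one scenario (outcomes improve, no mediator changes, each visit tested separately) under assumed correlations, and the documents do not supply them. The other starts from nine MRT-to-mediator tests (completion once, four utilization measures in two intervals), with a 27% chance of at least one false positive at correlation .5. That is not a false-mediation rate. It counts both directions, and unfavourable results make the MRT coefficient grow and so fail the rule; in the favourable direction it is about 14%.

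**Conclusion.** The point holds as a weakness in how 1c is decided. The text establishes the structure: about 90 chains (45 to 120 depending on reading), no lead chain, no error control, no definition of support, and a verdict ahead of the indirect-effect test.

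The size is conditional on the assumptions in the working. If MRT improves outcomes without changing any mediator, the false-claim rate is roughly 9–17%, or about 5–12% with a significant indirect effect required (lower if mediators and outcomes are only weakly related). If MRT affects nothing, it is about 1–12%. The case for a change does not depend on the exact multiple of 5%.

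A reader might infer that the trial's effectiveness conclusion is at risk. It is not: the tests of 1a and 1b do not pass through these chains. What is exposed is the explanation of how MRT works.

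**What to change.** Amend the mechanisms paragraph of section 5.6 before outcome data are examined.

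1. Conclude mediation only if the indirect effect is significant, and place that test before the verdict. State the method.
2. Name one lead chain for each mediator in 1c: MH RRTP completion, and one coding of continuing care. The sponsor chooses the outcome and visit in advance; PICTS GCT at 12 months is an example. That choice is one of scientific scope, because 1c also covers health outcomes and one of those could be a lead instead.
3. State that 1c is supported only if at least one lead indirect effect is significant. If indirect effects are tested without the total-effect step, apply Holm over the two at two-sided .05. If the present steps are kept, two unadjusted chains already stayed below 5% in simulation.
4. Report all other chains as exploratory estimates with confidence intervals and no verdict of support. This covers the other codings, the other visit, the interpersonal and peer mechanisms, and the health-outcome chains unless one is a lead.

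The cost is a few sentences, with no new data or patients. The lead chains lose a little power (each is tested at .025 at the first Holm step, where Holm applies), and the remaining chains lose confirmatory status.
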